49 research HPV. These samples will be sent to a laboratory where HPV typing is done by PCR
50 using the Anyplex™ II technology.
51 The study will focus on a sample of 400 young women. Participants must complete a
52 questionnaire containing demographic questions and their HPV immunization status.
53 Vaccination coverage expected in this population is about 50%. Depending on the state of
54 vaccination, two different groups will be vaccinated vs unvaccinated (200 women per group).
55 The cases of HPV infection are then calculated for each group and compared as a function
56 of the status of vaccination. Statistical tests will be applied McNemar's test for comparison
57 between the HPV prevalence rates between the 2 groups.

58

59 **Expected Results:** This study will allow us to confirm the possibility of using self-sampling
60 as a method of screening and monitoring of HPV infections in the general population, it will
61 also enable us to document the effectiveness of HPV vaccination by comparing prevalence
62 rate of HPV infections among a group of young girls vaccinated and not vaccine and assess
63 evolution of infection and clearance of HPV virus.

64 **Key words:** cervical cancer, self-sampling, Human papillomavirus (HPV)

65

66 1. Background

67 Human papillomavirus (HPV) vaccination to prevent cervical cancer has been introduced in
68 Switzerland in 2008. Recommendations are that young girls aged 11 to 14 are included in
69 the immunization schedule program at school and girls aged 15 to 19 are included in a
70 “catch-up program”, for a transition period, until 2012. Within school-based program, the
71 vaccine uptake has been achieved to date with a 60% course completion, but lower rate
72 (20%) has been observed in cantons having adopted an “opportunistic” vaccination strategy.
73 Monitoring public health impact is an essential component of the intervention. Since the
74 eventual cervical cancer disease reduction will be only able to be evaluated decades after
75 exposure, current monitoring activity will focus on the anticipated earlier reduction of HPV
76 vaccine-type in the population. In 2015, seven years passed since the first vaccinated
77 cohorts entered the program; “school-vaccinated” women will be of 18 years old and “catch-
78 up vaccination” will be of 32 years old. Prior introduction of the vaccine in Switzerland, the
79 only available data was from HPV testing performed with residual cervical screening sample

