148 Genève and Faculty of Medicine at the University of Geneva.

149 • Understands study procedures and accepts voluntarily to participate by signing the
150 informed consent form (ICF)

151

152 ***Exclusion criteria:***

153 • History of hysterectomy or treatment on the cervix during the last 12 months.

154

155

156 **Study Design and Methods**

157

158 Setting: The study will be conducted in collaboration with the High school of health in Geneva
159 and Faculty of Medicine at the University of Geneva. The study will be proposed to 400
160 women attending these schools.

161

162 Recruitment: It will take place in the health school of health and Faculty of Medicine at the
163 University of Geneva. Trial information on the University website will be available; it will also
164 contain a phone number for helpline. Cards to check eligibility, registration and scheduling
165 will be available. The HPV self-collection kit will be directly distributed to participants at the
166 end of their courses to School of Health and University of Geneva School of Medicine

167

168 Data collection: Vaccination status, age, menopausal status, marital status, parity, tobacco
169 consumption, medical records, geographic data, consulting-date and HPV-test result.

170

171 HPV tests: The HPV self-collection kit included a dacron swab, collection tube, instructions
172 with explanatory pictures, consent forms and a participant demographic information. The

173 HPV analysis will be performed by Real-time PCR. Delay between sampling and lab
174 processing will be noted.

175

176 Technical aspect: Written informed consent will be obtained by papier. All women will
177 perform a self sampling for HPV testing using a simple swab with no medium. The results of
178 HPV testing and sociodemographic data will be archived in a database.

179

180 Statistical analysis: The expected vaccination coverage in this population is about 50%.
181 According vaccination status, 2 different groups will be formed (vaccinated vs non-
182 vaccinated). The cases of HPV infection (status HPV+) will then be calculated for each group
183 and compared according to the vaccination status. The applied statistical tests will be
184 McNemar's test for comparison.

185

186 Sample size: Sample size was obtained based on estimated prevalence of 6% of HPV 16/18
187 infection in the Swiss population aged less than 30 years. A total of 200 specimens per group

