188 would be needed to detect about an 85% reduction in HPV 16/18 prevalence (prevalence of
189 0.9% in the vaccinated population), given an 80% power and a two-sided significance level of
190 95% (based on representative data from England). We therefore estimate that a sample size
191 of 400 women (200 in each group) will be adequate for the analyses.

192

193 Follow up: Participants will receive their results by e-mail directly via our colposcopy nurse.
194 We will follow the HPV-positive participants every 6 months during 5 years to assess the
195 evolution of their HPV status and the viral clearance. In order to do this, every 6 months they
196 will receive a self-sampling HPV kit at home, which they will return by mail to the
197 HUG for analysis.

198

199

200 **4. Statement regarding the relevance and potential contribution of the project to** 201 **cancer control**

202 Data from the registries will be used to assess the HPV prevalence of the pre-vaccine era
203 and will be the basis for monitoring infection after post-vaccine introduction. This study will
204 provide important data about the prevalence of HPV infection in a young and sexually active
205 population of women and on the proportion of vaccinated and non-vaccinated young women.

206 Despite the impact of vaccine on invasive cancers is not expected until some decades after
207 its extensive implementation, as the type-specific prevalence of HPV infection is very high in

208 young sexually active populations, the effect of a successful HPV vaccination program
209 should be quickly detected by sentinel surveillance in this sub-population.

210 Monitoring the impact of the vaccination programs by detecting type-specific infection is
211 important as it is the earliest anticipated change, and failure to detect protection from
212 infection will indicate failure to prevent cancer in the subsequent decades and allow the
213 implementation of appropriate changes in cervical cancer screening strategies.

214 This surveillance is required in order to document the expected gains in cancer prevention if
215 there is appropriate population coverage. In our case, no data is available in Switzerland.
216 Such surveillance would allow further studies to determine the duration of protection, long-
217 term safety and actual impact on health-care cost consumption.

218 In this project, 400 young girls will know their statuses for HPV infection and will obtain

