219 information about this prevalent infection and offered sexual counselling. Those who test
220 positive for HPV infection will be guided to a gynaecological consultation for adequate
221 management.

222 By using self-sampling for HPV testing, we will demonstrate the potential benefit in terms of
223 participation, lower cost and feasibility to determine the prevalence of infection. This method
224 is much easier and cheaper than the current cervical cancer screening test used (Pap test),
225 which requires a gynaecological consultation. The self-sampling could be used to increase
226 the participation of young women in the cervical cancer screening programs and thereby
227 increase the effectiveness of the overall program screening.

228 In conclusion, monitoring HPV prevalence among sexually active young women in different
229 selected settings will provide an important early indication of HPV vaccine impact. These
230 data will also contribute to add important information for cervical cancer screening.

231

232 **5. Ethical issues**

233 The investigators commit that this study will be conducted in accordance with the Swiss law,
234 as well as in accordance with the recommendations of Good Clinical Practices (ICH E6-
235 1996) and the Declaration of Helsinki (Fortaleza, October 2013). Before the study starts, the
236 approval of the protocol by the Geneva Ethics Committee will be required, and all patients
237 will give their written informed consent to participate in the study.

238 All the participants will be informed of the HPV results and a webpage containing information
239 on the implications of having a positive result in women aged less than 30 years will be
240 available. Information can also be obtained via our colposcopy nurse (a helpline will be
241 available).

242

243 **6. Financial consideration**

244

245 This study includes no charge for the patients. Financial support was solicited for a 100%
246 research nurse for 12 months period (FRS 135'000), to buy kit sampling HPV (FRS 60) and
247 to Cepheid GeneXpert® System for HPV testing (equipment rental + Test cartridges) (FRS
248 40'000).

[figure not shown]
249

250 **7. References**

251 1. Petignat P, Faltin D, Goffin F, Billieux MH, Stucki D, Sporri S, et al. Age-related performance of
252 human papillomavirus testing used as an adjunct to cytology for cervical carcinoma screening in a
253 population with a low incidence of cervical carcinoma. *Cancer*. 2005;105(3):126-32.

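### The vaccinated/unvaccinated comparison is by vaccination status alone, and no sexual-exposure item is named among the planned data, although the protocol describes a sexually active population

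*Protocol*

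**What the plan says.** Eligibility (section 3) rests on age 18 to 31, attendance at the named schools, consent, and no hysterectomy or recent cervical treatment. Sexual activity is not a criterion.

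The variables are listed under Data collection: "Data collection: Vaccination status, age, menopausal status, marital status, parity, tobacco" "consumption, medical records, geographic data, consulting-date and HPV-test result". The Abstract describes the instrument as a "questionnaire containing demographic questions and their HPV immunization status". Under Technical aspect, the results of "HPV testing and sociodemographic data will be archived in a database". None of these names sexual debut, sexual activity or number of partners.

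Under Statistical analysis, HPV-positive cases are counted in each group "and compared according to the vaccination status. The applied statistical tests will be" McNemar's. No stratification, matching or adjustment is described.

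Section 4 says the study will "provide important data about the prevalence of HPV infection in a young and sexually active" population, and its closing paragraph begins "In conclusion, monitoring HPV prevalence among sexually active young women in different". Section 2 aims to document the effectiveness of vaccination on HPV prevalence, and one of the listed secondary objectives is to generate data on vaccination impact.

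**The concern.** The groups are formed by who happened to be vaccinated, not by randomisation. HPV is sexually transmitted, so the share of women ever exposed drives prevalence in each group. If that share differs between the groups, a difference in prevalence, or its absence, can reflect exposure rather than the vaccine.

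The protocol describes its population as sexually active, but as written it neither selects such women nor names an item that would identify them. Section 4 also attaches weight to the result: it treats a failure to detect protection as a sign that cancers will not be prevented, and as grounds for changing screening strategy. That reading needs groups comparable on exposure, or at least a way to check whether they are.

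This differs from an adjustment method that a statistical analysis plan can supply later. Such a plan can use age, which is collected. It cannot use exposure if nobody asked about it.

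**Working it through.** **Plan's own figure.** Inputs from Sample size: HPV 16/18 prevalence 6% against 0.9% (an 85% reduction, 1 − 0.9/6), 80% power, two-sided 5% (the text prints 95%, read here as its complement). The pooled-variance formula for two independent proportions, without continuity correction, gives 200 per group, as stated. The sizing is not in dispute.

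**Method for the illustrations.** Rejection rates come from exact enumeration of the uncorrected chi-square test, two-sided 5%, 200 against 200. This is a two-independent-group test, in line with the sizing. On this method the plan's 6% against 0.9% has 85% power, and the false-positive rate at 6% in both groups is 4.7%.

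**Assumptions not in the document.** Never-active women have no HPV 16/18. Of unvaccinated women, 95% are active and their overall prevalence is 6%, so prevalence in active women is 6%/0.95 = 6.32%. All activity rates are assumed.

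**No vaccine effect.** Vaccinated prevalence = 6.32% × share of vaccinated women active. Apparent reduction = 1 − share/0.95.

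| Vaccinated active | Vaccinated prevalence | Unvaccinated prevalence | Apparent reduction | False-positive rate |
|---|---|---|---|---|
| 90% | 5.68% | 6.00% | 5% | 4.9% |
| 80% | 5.05% | 6.00% | 16% | 6.6% |
| 70% | 4.42% | 6.00% | 26% | 10.5% |
| 60% | 3.79% | 6.00% | 37% | 17.0% |

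With the two groups' activity rates swapped, the rejection rates are the same and the bias runs the other way: 95% of vaccinated against 60% of unvaccinated women active gives a ratio of 0.95/0.60 = 1.58.

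**True 85% reduction.** Apparent reduction = 1 − 0.15 × (vaccinated share active)/(unvaccinated share active).
- 90% of vaccinated against 70% of unvaccinated active: 1 − 0.15 × 0.90/0.70 = 81%.
- 70% of vaccinated against 95% of unvaccinated active: 1 − 0.15 × 0.70/0.95 = 89%.

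An effect as large as the planned one is therefore little distorted. A small or null effect could be materially misread.

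**Comparison in active women only, true 85% reduction.**
- Balanced activity, overall unvaccinated prevalence held at 6%: 190 against 190, or 140 against 140, gives 85% power, so nothing is lost.
- Unbalanced activity, 140 vaccinated against 190 unvaccinated: 0.15 × 6.32% = 0.95% against 6.32% gives 76%. With no vaccine effect, the false-positive rate in that comparison is 4.7%.

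**Ages.** Section 1 places catch-up at ages 15 to 19 from 2008. A woman of 19 in 2008 is 19 + 7 = 26 in 2015, yet the same section puts catch-up women at 32 in 2015. Eligibility runs to 31, and the sizing prevalence refers to women under 30.

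**The case against.** **The record is incomplete.** Medical records are listed without content, and the questionnaire itself is not shown. A reader might infer that exposure will not be collected. The documents do not prove this; they show only that it is not named as planned data. This stands and limits the claim. Marital status and parity are at most weak proxies.

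**Later contact exists.** Because of "We will follow the HPV-positive participants every 6 months during 5 years to assess the" course of infection, a reader might infer that HPV-negative women are never contacted again. That is not so: section 3 has participants receive results by e-mail, and sections 4 and 5 add counselling and a helpline. What is limited to HPV-positive women is repeat sampling. Asking about exposure after a woman knows her result would still risk reporting bias, so baseline remains the right time.

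**Power.** A reader might also infer that imbalance would badly damage power. With a true 85% reduction, and 90% of vaccinated against 70% of unvaccinated women active at 6.32% prevalence in active women, crude power is 63%. But unvaccinated prevalence there has dropped to 4.42%. Balanced 70% activity at the same prevalence in active women already gives 71%. Holding unvaccinated women at the plan's 6% gives 1.16% against 6.00% and 79%, against 85% for the plan's own figures. Most of the fall to 63% is lower baseline prevalence, so that figure should not be used as the cost of imbalance.

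**Scope.** The comparison serves a secondary objective, and section 4 frames the work as sentinel surveillance. This tempers the weight of the point but does not remove it, because section 2 speaks of documenting effectiveness.

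**Conclusion.** The point holds as a cheap, time-sensitive improvement. The comparison is by vaccination status alone, and no sexual-exposure item is named in eligibility, data list, questionnaire or database, although the protocol describes a sexually active population and aims to document effectiveness.

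No activity rate or gap is given, so neither the size nor the direction of bias can be derived. Under the assumed gaps of 15 to 35 points, a null effect would look like a reduction of 16% to 37%; a 5-point gap is negligible. The documents do not support the stronger reading that the comparison is invalid or biased in a known direction.

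The age statements are a side matter. They need reconciling, but age is collected, and adjusting for it is ordinary analysis-plan content. The primary feasibility aim is unaffected.

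**What to change.** 1. Before enrolment, add three items to the baseline questionnaire and name them under Data collection: ever sexually active, number of partners and, for those active, age at first intercourse. If the questionnaire or the medical records already hold them, say so.
2. State that the two-independent-group comparison will be repeated in women who report being sexually active.
3. As a side note, reconcile the four age statements: catch-up at 15 to 19, catch-up women aged 32 in 2015, eligibility at 18 to 31, and a sizing prevalence for women under 30.

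The cost is a few sensitive questions and some analysis wording. The restricted comparison loses no power when activity is balanced and overall prevalence stays at 6%. It loses some when activity is unbalanced, for example 76% at 140 against 190. With about 200 × 6% + 200 × 0.9% = 13.8 expected HPV 16/18 cases, any model should carry no more than one or two covariates, so restriction is the simpler use of the new data.

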108 gynecological hospital visits. This method is certainly effective, but expensive, furthermore
109 screening coverage is still insufficient (only 30 to 40 % women's don't participate at the
110 screening) in Switzerland. Also a part of our study population don't participate in screening
111 such young people of foreign origin for various reasons, no gynecological medicine,
112 economic cost etc ...

113 Several studies raise the effectiveness and efficiency (9) of the self sampling to increase
114 screening coverage (10), participation rate of nonattenders (11, 12) self-sampling has been
115 nearly as sensitive as clinician-obtained cervical samples and more sensitive than cytology
116 for the detection of cervical intraepithelial neoplasia (CIN) for lesions of high-grade CIN-II or
117 higher (CIN-II+) (13-14) .

118 Through this study we want to evaluate the possibility of using self sampling as a screening
119 tool in a real population, yet a study in Geneva showed the possibility of its use for screening
120 a population not visiting gynecological hospital visits (15), but the actual population use
121 remains to be demonstrated.

122 **2. Objectives**

123 Through this study, we evaluate the possibility to use self sampling as a screening tool in a
124 real population, document the effectiveness of this vaccination on the prevalence of HPV
125 infections and assess evolution of infection and we will assess the evolution of viral
126 infection and clearance of throughout 5 years in a population of young, unvaccinated and
127 vaccinated girls.

128

129 **Primary objective**

- 130 • Explored the feasibility of establishing a home-based Self-HPV screening strategy in
131 general population

132

133 **Secondary objective**

- 134 • To determine the HPV prevalence of vaccine-type: 19 high-risk HPV types (16, 18, 26,
135 31, 33, 35, 39, 45, 51, 52, 53, 56, 58, 59, 66, 68, 69, 73, 82) and 9 low-risk HPV types(6,

136 11, 40, 42, 43, 44, 54, 61, 70) in young women population attending High schools in
137 Geneva and Faculty of Medicine at the University of Geneva.

138 • To generate data about vaccination impact and vaccine coverage.

139

140 • To assess the infection's evolution and clearance of HPV throughout 5 years in a
141 population of young, unvaccinated and vaccinated young women

142

143

144 **3. Material and method**

145

146 ***Inclusion criteria:***

147 • Eligible women aged between 18-31 years attending of Haute Ecole de Santé –

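### The vaccinated/unvaccinated comparison is written for any HPV positivity, but the sample size and its 80% power are for HPV 16/18 only

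*Protocol*

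**What the plan says.** Section 3, Statistical analysis, splits the women by vaccination status and then states: "vaccinated). The cases of HPV infection (status HPV+) will then be calculated for each group". The groups are compared on that count. The abstract has the same unrestricted outcome: "The cases of HPV infection are then calculated for each group and compared as a function".

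The scope of typing is set in section 2, secondary objective: "To determine the HPV prevalence of vaccine-type: 19 high-risk HPV types (16, 18, 26", with further types listed, "and 9 low-risk HPV types(6" and others. That makes 19 + 9 = 28 types, all under the vaccine-type label.

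The Sample size paragraph of section 3 uses a narrower outcome: "Sample size was obtained based on estimated prevalence of 6% of HPV 16/18" infection, with 200 specimens per group that "would be needed to detect about an 85% reduction in HPV 16/18 prevalence (prevalence of" 0.9% in vaccinated women), at 80% power and two-sided. It concludes that 400 women suffice for the analyses. The protocol nowhere names an HPV 16/18 comparison as the analysis, and it gives no prevalence or power for any HPV.

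**The concern.** The outcome that is powered and the outcome that is to be compared are different. A vaccine that acts on types 16 and 18 lowers any-HPV positivity only by the share of women whose sole infection was 16 or 18. The remaining types add about the same number of positives to both groups. This raises the variance and, through co-infection, also narrows the absolute difference.

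The protocol's own rationale points to the narrower outcome. The background reports the effect on infection as a fall in HPV 16/18, and section 4 describes monitoring through type-specific infection. The analysis paragraph does not carry this through.

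The consequence matters because section 4 says in advance how a negative finding would be read: undetected protection against infection is taken to mean that cancer will not be prevented, and it is linked to changes in screening strategy. An analysis on a diluted outcome could give that result even if the vaccine removed 85% of 16/18 infections.

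**Working it through.** **Inputs from the protocol (section 3, Sample size):** HPV 16/18 prevalence 6% unvaccinated and 0.9% vaccinated; 200 per group; 80% power; two-sided. The stated significance level of 95% is read as α = 0.05.

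**Test used here.** The protocol names McNemar's test, which is for paired data. These are independent groups, so the calculation uses the comparison of two independent proportions (pooled variance under the null, no continuity correction).

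**Step 1: reproduce the stated sample size.** With p̄ = (0.06 + 0.009)/2 = 0.0345,

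n = [1.960·√(2·0.0345·0.9655) + 0.842·√(0.06·0.94 + 0.009·0.991)]² / (0.06 − 0.009)²

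= (0.5059 + 0.2151)² / 0.002601 = 199.9, so 200 per group, with power 80.0%. The stated figure is right for HPV 16/18.

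**Step 2: the same design on any HPV.** The prevalence of the other types, q, is not in the protocol and is assumed over a range. If q is equal in both groups and independent of 16/18, any-HPV prevalence is 1 − (1 − q)(1 − p), with p = 0.06 or 0.009. Example for q = 10%: 1 − 0.90·0.94 = 15.4% and 1 − 0.90·0.991 = 10.8%. The difference is 4.6 points, the standard error is 0.0337 under both hypotheses, and power = Φ[(0.0459 − 1.960·0.0337)/0.0337] ≈ 27%.

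| q | Any HPV, unvaccinated vs vaccinated | Relative reduction | Power, 200 per group | n per group for 80% |
|---|---|---|---|---|
| 0% | 6.0% vs 0.9% | 85% | 80% | 200 |
| 5% | 10.7% vs 5.9% | 45% | 42% | 507 |
| 10% | 15.4% vs 10.8% | 30% | 27% | 848 |
| 20% | 24.8% vs 20.7% | 16% | 16% | 1657 |
| 30% | 34.2% vs 30.6% | 10% | 12% | 2698 |

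Exact binomial power of the uncorrected chi-square test agrees closely for q of 5% and above (41.5%, 27.4%, 16.4%, 11.9%). For 16/18 itself the exact figure is 85% with that test and 77% with Fisher's test.

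**Step 3: assumptions more favourable to the plan.**

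- *No co-infection*, so the full 5.1-point difference is kept. With any-HPV prevalence of 10%, 15%, 20%, 30% and 40% in unvaccinated women, power is 49%, 34%, 27%, 21% and 18%.
- *The vaccine also lowers all other types by 20%* (independence as in step 2). Power is about 59%, 52%, 51% and 55% at q = 5%, 10%, 20% and 30%.
- *The same with a 30% reduction.* Power is about 67%, 66%, 71% and 80% at those values of q, and about 88% at q = 40%.

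**The case against.** HPV positivity is never defined. The figure of 28 types comes from a prevalence objective, not from the analysis paragraph, and the protocol names two test systems (Anyplex II in the abstract, GeneXpert in section 6). The background speaks of vaccine-type infection, section 4 of type-specific infection, and the sample size paragraph directly after the analysis paragraph names 16/18. One could therefore call the outcome undefined rather than wrong, and expect an analysis plan to define it. This stands in part: 28 types is the plain reading, not an explicit definition. But both places that describe the comparison leave the type open, and no wording limits it to 16/18. An analysis plan that followed the protocol would inherit the broader outcome.

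The power loss also rests on assumed values. The absence of cross-protection cited in the background concerns countries with coverage below 50%, while this study expects about 50%, and the background also reports falls in anogenital warts. Zero effect on all other types is thus an assumption of this review, and step 3 shows how much it matters. Power returns to 80% only with a reduction of about 30% in all other types combined with q of 30% or more. The protocol assumes no such effect.

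Finally, the comparison serves a secondary objective, since feasibility is primary, and no data would be lost. That lowers the stakes, but this comparison is the sole basis for the 400 women.

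**Conclusion.** The point holds. The 80% power applies to HPV 16/18 and not to the comparison as written. If the vaccine acts only on 16/18, power for any HPV at 200 per group is about 42% when other types have 5% prevalence and about 12% at 30%. Without co-infection it is 49% or less once any-HPV prevalence in unvaccinated women reaches 10%. These sizes depend on a prevalence the protocol does not give, on α read as 0.05, and on a test for independent proportions in place of McNemar's test. The loss of power holds throughout unless the vaccine also has a sizeable effect on the other types. The vaccine-type label on all 28 types is a smaller, editorial fault that adds to the confusion.

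**What to change.** In section 3, Statistical analysis, and in the abstract, state that the powered vaccinated/unvaccinated comparison is on HPV 16/18 positivity, the outcome used for the sample size. State that any-HPV positivity and the remaining types are compared as secondary, descriptive results, with no claim of 80% power. Prevalence of all listed types can still be reported as the objective asks. In section 2, reword the objective so that vaccine-type does not cover all 28 types.

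If the investigators do want any HPV as the main comparison, they should state the expected prevalence in both groups and recalculate; under the assumptions of step 2 this means roughly 500 to 2,700 women per group.

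The recommended change costs a protocol wording amendment. It needs no extra participants or samples, because HPV typing is already planned.
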